# 1 Introduction

Objectives	
1 Primary Objective
 
To compare the effects of knee OA educational information, with and without pathoanatomical content, on i) beliefs about the necessity to have an x-ray to confirm an OA diagnosis, and ii) beliefs about the necessity of joint replacement surgery in adults who have not had a knee joint replacement.
 
2 Secondary Objectives
 
To compare the effects of knee OA educational information, with and without pathoanatomical content, on management beliefs (about exercise and physical activity, the safety of exercise, medications, x-rays to determine treatment), level of concern, and OA knowledge in adults who have not had a knee joint replacement.
 
To explore whether a history of knee pain in the last 3 months moderates the effect of knee OA educational information without pathoanatomical content on the two primary outcomes, i) beliefs about the necessity to have an x-ray to confirm an OA diagnosis, and ii) beliefs about the necessity of joint replacement surgery in adults who have not had a knee joint replacement.

Study Design	Two-arm, parallel groups superiority randomised controlled trial.
Planned Sample Size	556 participants.
Study Procedures	
The entire trial will be administered in one single online survey. Participants will initially complete screening questions within the survey to determine eligibility. Eligible participants will then complete baseline outcome measures before being randomly allocated to one of two groups, both of whom will then be asked to immediately read a digital information pamphlet about knee OA on screen:
 
i) Control group: the pamphlet will contain information about OA including biological pathoanatomical information and language about OA
 
ii) Experimental group: the same pamphlet as the Control group, but with all pathoanatomical information and language relating to the structure of an OA joint removed.

	
All participants will complete outcome measures again, immediately after reading their allocated digital information pamphlet.

Duration of the study
	
Anticipated participant recruitment start: June 2022  Anticipated data collection end: June 2022
 
Based on our previous similar study [1], which recruited 735 participants in four days through a similar mechanism, we anticipate recruitment for this RCT will take approximately 6 days.

Figure 1. Study chart

## 2 Data Source

Participant recruitment will be managed by an external company, Cint Pty Ltd. Data security will be managed according to their data privacy and security protocols.

Data collection will be managed wholly online through Qualtrics, an electronic data capture system. Qualtrics is a secure web application for building and managing research questionnaires and databases. The University of Melbourne holds a licence for staff use of Qualtrics and surveys and associated data will only be accessible via secure login by the study research staff.

### *Re-identifiable/coded data*

Questionnaires will be completed electronically and anonymously, with no identifying information being recorded. Electronic data will be stored in the Qualtrics website, accessible only to the study research staff by password protection. Data from within Qualtrics will eventually be exported to Microsoft Excel and other statistical packages used by the researchers for analyses and stored securely on password-protected servers accessible only to the study research staff.

## 3 Analysis Objectives

The aim of this study is to compare the effects of knee OA educational information, with and without pathoanatomical content, on consumer OA management beliefs in adults who have not had a knee joint replacement.

### 3.1 Aim 1

To compare the effects of knee OA educational information, with and without pathoanatomical content, on i) beliefs about the necessity to have an x-ray to confirm an OA diagnosis, and ii) beliefs about the necessity of joint replacement surgery in adults who have not had a knee joint replacement.

We hypothesise that removing pathoanatomical content will lead to lower beliefs that an x-ray is necessary to confirm an OA diagnosis and lower beliefs that joint replacement surgery is necessary, compared to information with pathoanatomical content.

### 3.2 Aim 2

To compare the effects of knee OA educational information, with and without pathoanatomical content, on management beliefs (about exercise and physical activity, the safety of exercise, medications, x-rays to determine treatment), level of concern, and OA knowledge in adults who have not had a knee joint replacement.

We secondarily hypothesise that removing pathoanatomical content will lead to higher beliefs that exercise and physical activity is necessary and is safe, lower beliefs that medication is necessary, lower beliefs that x-rays are required to determine treatment, lower levels of concern, and higher OA knowledge.

To explore whether a history of knee pain in the last 3 months moderates the effect of knee OA educational information without pathoanatomical content on the two primary outcomes, i) beliefs about the necessity to have an x-ray to confirm an OA diagnosis, and ii) beliefs about the necessity of joint replacement surgery in adults who have not had a knee joint replacement.

## 4 Analysis sets/Populations/Subgroups

Inclusion Criteria

Participants will be eligible for the study if they meet the following inclusion criteria:

- i) Aged 45 years or over;
- ii) Have (n=278), or have not (n=278), experienced any activity-related knee joint pain in the past 3 months;
- iii) Currently living in Australia.

#### Exclusion Criteria

Participants will be ineligible for the study if they have:

- i) Inability to understand or read English;
- ii) Have had a joint replacement in any of their knee joints.

## 5 Endpoints and Covariates

All variables are listed in Appendix 1 and the coding of the derived variables can be found in Appendix

2. Outcome measures are also provided in the table below.

Primary outcome measures		
Belief about x-ray to diagnose knee OA	
Baseline: If you were told by your doctor that you had knee osteoarthritis, would you think an x-ray is necessary to confirm the diagnosis?
 
Post-intervention: Having read the information sheet, if you were told by your doctor that you had knee osteoarthritis, would you think an x-ray is necessary to confirm the diagnosis?
	11-point Numeric Rating Scale (NRS) ranging from 0=definitely unnecessary to 10=definitely necessary
Belief about joint replacement surgery	
Baseline: If you were told by your doctor that you had knee osteoarthritis, would you think joint replacement surgery (to replace the affected joint with an artificial joint) is necessary for your knee at some stage?
 
Post-intervention: Having read the information sheet, if you were told by your doctor that you had knee osteoarthritis, would you think joint replacement surgery (to replace the affected joint with an artificial joint) is necessary for your knee at some stage?
	11-point NRS ranging from 0=definitely unnecessary to 10=definitely necessary
Secondary outcome measures		
Beliefs about treatment options		
Belief about exercise and physical activity	
Baseline: If you were told by your doctor that you had knee osteoarthritis, would you think exercise and physical activity is helpful to manage it?
 
Post-intervention:
	11-point NRS ranging from 0=definitely not helpful to 10=definitely helpful

	Having read the information sheet, if you were told by your doctor that you had knee osteoarthritis, would you think exercise and physical activity is helpful to manage it?	
Belief about safety of exercise	
Baseline: If you were told by your doctor that you had knee osteoarthritis, would you think exercise and physical activity would damage your knee?
 
Post-intervention: Having read the information sheet, if you were told by your doctor that you had knee osteoarthritis, would you think exercise and physical activity would damage your knee?
	11-point NRS ranging from 0=definitely would not damage it to 10=definitely would damage it
Belief about medication	
Baseline: If you were told by your doctor that you had knee osteoarthritis, would you think medication is helpful to manage your knee symptoms?
 
Post-intervention: Having read the information sheet, if you were told by your doctor that you had knee osteoarthritis, would you think medication is helpful to manage your knee symptoms?
	11-point NRS ranging from 0=definitely not helpful to 10=definitely helpful
Belief about x-ray to determine treatment	
Baseline: If you were told by your doctor that you had knee osteoarthritis, would you think an x-ray is necessary to determine the best treatment for your knee?
 
Post-intervention: Having read the information sheet, if you were told by your doctor that you had knee osteoarthritis, would you think an x-ray is necessary to determine the best treatment for your knee?
	11-point NRS ranging from 0=definitely unnecessary to 10=definitely necessary
OA Knowledge		
Knee Osteoarthritis Knowledge Scale	
An 11-item questionnaire with the following questions:
 
 
1. Your knee joint wears out with everyday use
 
2. Osteoarthritis will only get worse over time
 
3. Increased knee pain always means that you have damaged your knee
 
4. You need an x-ray or scan to know if you have osteoarthritis
 
5. Being active makes osteoarthritis feel better
 
6. Keeping a healthy body weight is a key part of osteoarthritis care
 
7. X-rays or scans show how much your osteoarthritis affects you
 
8. Making your leg muscles stronger improves your ability to do daily tasks
 
9. Pain from osteoarthritis can be managed without surgery
 
	
Each statement rated as False (1), Possibly False (2), Unsure (3), Possibly True (4), or True (5). Each item is scored on a scale from 1 to 5. Items 1,2, 3, 4, 7, and 11 are reverse scored and added to items 5, 6, 8, 9, and 10. Scores range from 11-55 with higher scores indicating greater/more accurate knowledge about osteoarthritis.
 
Measured at baseline and post-intervention.

	
10. Exercises can ease pain as much as most medications
 
11. Most people with knee osteoarthritis will need a joint replacement at some point
	
Level of concern		
Level of concern	
Baseline: If you were told by your doctor that you have knee osteoarthritis, how concerned would you be that your knee problem would get worse in the future?
 
Post-intervention: Having read the information sheet, if you were told by your doctor that you have knee osteoarthritis, how concerned would you be that your knee problem would get worse in the future?
	
4-point Likert scale with response options: Not at all concerned A little concerned Quite concerned Very concerned

## 6 Handling of Missing Values and Other Data Conventions

If missing data are present, an appendix table will provide summaries of baseline characteristics and baseline levels of primary and secondary outcomes where measured between two groups: those participants who provide both primary outcomes post-intervention, and those participants who are missing either or both primary outcomes. If less than 5% of both primary outcomes is missing, analyses will be performed on complete case data. If greater than 5% of either primary outcome is missing, multiple imputation will be applied for the primary analysis. Missing outcomes will be imputed using chained equations with predictive mean matching and five nearest neighbours for continuous outcomes. Imputation models for continuous outcomes post-intervention will include all primary and secondary outcomes at both baseline and post-intervention, along with age, gender, BMI, education level, state, ethnicity, financial situation, exercise/physical activity participation, care-seeking, knee pain, prior knee surgery, regular pain relief for musculoskeletal condition, and health literacy. Data will be imputed for each treatment group separately. The number of imputed data sets created will be based on the percentage of patients in the sample with missing outcome data (e.g., 15 imputed datasets if 15% of participants have missing data). Estimates from the imputed datasets will be combined using Rubin's rules [2].

## 7 Statistical Methodology

### 7.1 Statistical Procedures

A biostatistician ([name], supervised by [name]) will analyse de-identified data in Stata version 16.1 (StataCorp LLC, College Station, TX, USA), while blind to group name. Descriptive data will be presented by intervention group as mean (SD), median (IQR) or n (%) as appropriate. Comparative analyses between groups will be performed using intention-to-treat according to the group to which the participant was randomised, irrespective of whether they adhered to the intervention by reading the information. The number included in each analysis will be reported. Standard diagnostic plots will be used to check model assumptions, including assessing linearity and homoscedasticity, where appropriate.

#### 7.1.1 Aim 1

Separate linear regression models for each primary outcome will be used to estimate the between-group mean (95% confidence interval, CI) difference in post-intervention scores, adjusted for the outcome at baseline. Post-intervention time point was 'immediately following reading a digital information pamphlet about knee OA on screen'.

#### 7.1.2 Aim 2

Separate linear regression models for each continuous secondary outcome will be used to estimate the between-group mean (95% CI) difference in post-intervention scores, adjusted for the outcome at baseline. For the ordinal secondary outcome, level of concern, ordinal logistic regression models will be fitted similarly, adjusted for the outcome at baseline. The proportional odds assumption will be assessed using the Brant test. If proportional odds cannot be assumed, multinomial regression models will be fitted. Results will be reported as odds ratios, or relative risk ratios if multinomial regression is used, with corresponding 95% CIs.

The mean (95% CI) effect on each of the primary outcomes, i) beliefs about x-rays and ii) beliefs about joint replacement surgery, of potential moderators, i) a history of knee pain in the past 3 months, ii) highest education level (as a binary variable, no tertiary versus some tertiary) and iii) ever sought care for knee pain from any healthcare provider for each group will be estimated using separate linear regression models for each outcome and each moderator, with an interaction term fitted between group and the potential moderator, adjusting for baseline scores of the relevant primary outcome.

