## 7.2 Measures to Adjust for Multiplicity, Confounders, Heterogeneity

We have two primary outcomes and so have adjusted the alpha for each primary outcome to 0.025 to give an overall alpha of 0.05 across both outcomes. We have several secondary outcomes. All secondary outcomes are exploratory and not powered for. We will therefore not adjust for multiple secondary outcomes but instead report all effect sizes, confidence intervals, and p values in order to let readers use their own judgment about the relative weight of the conclusions. This approach aligns with the usage of p-values favoured by the American Statistical Association [3].

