f Ordinal logistic regression model fitted, adjusted for the outcome at baseline where able, as proportional odds could be assumed. Odds ratio > 1 indicate increased odds of Group 2 compared to Group 1. g Multinomial regression model fitted, adjusted for the outcome at baseline where able, as proportional odds could not be assumed. Relative risk ratios > 1 indicate increased risk of Group 2 compared to Group 1.

\*Measured using the 11-point numerical rating scale ranging from 0='definitely unnecessary' to 10='definitely necessary'.

‡ Measured using the 11-point numerical rating scale ranging from 0='definitely not helpful' to 10='definitely helpful'.

β Measured using the 11-point numerical rating scale ranging from 0='definitely would not damage it' to 10='definitely would damage it'.

§ Measured using the Knee Osteoarthritis Knowledge Scale [4]. Scores range from 11 to 55, with higher scores indicating greater knowledge about osteoarthritis.

h Question asked "if you were told by your doctor that you have knee osteoarthritis, how concerned would you be that your knee problem would get worst in the future?"

**Table 3: Moderation of the effect of the removal of pathoanatomical content in knee osteoarthritis educational information on primary outcomes using complete case data.**

Outcome	Potential moderators at baseline	Group 1 Mean (SD) [n=xxx]	Group 2 Mean (SD) [n=xxx]	Group 2 – Group 1 Mean (95% CI) [n=xxx]	Interaction p-value
Belief x-ray is necessary for diagnosis *	Knee pain in the last 3 months				
	No				
	Yes				
	Highest education level#				
	No tertiary				
	Some tertiary				
	Ever sought care for knee pain from any healthcare provider				
	No Yes				
Belief joint replacement surgery is necessary at some stage *	Knee pain in the last 3 months				
	No				
	Yes				
	Highest education level#				
	No tertiary				
	Some tertiary				
	Ever sought care for knee pain from any healthcare provider				
	No Yes				

SD=standard deviation; CI=confidence intervals.

\*Measured using the 11-point numerical rating scale ranging from 0='definitely unnecessary' to 10='definitely necessary'.

#Highest education level as a binary variable, no tertiary (primary school, secondary school, trade or trade certificate and don't know/unsure) versus some tertiary (university or tertiary institute and higher university degree).

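### The Table 3 moderator models pool one residual variance over both moderator levels and the homoscedasticity check has no stated consequence, so the within-level confidence intervals, and the interaction p-values for education and care-seeking, can be modestly off (minor)

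*SAP*

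**What the plan says.** Section 7.1.2 examines three binary moderators (knee pain in the past 3 months, education, ever having sought care) for each of the two primary outcomes. Each of the six linear models is adjusted for the baseline score, "with an interaction term fitted between group and the potential moderator". No robust or level-specific variance is named, so the natural reading is the default in Stata: one residual variance for the whole model.

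The outcomes are bounded. Section 5 gives both as an "11-point Numeric Rating Scale (NRS) ranging from 0=definitely unnecessary to 10=definitely necessary".

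On model checking, Section 7.1 states: "Standard diagnostic plots will be used to check model assumptions, including assessing linearity and homoscedasticity, where appropriate". It does not say what happens if the plots show unequal variance. The ordinal model in Section 7.1.2, by contrast, has both a check (the Brant test) and a fallback (multinomial regression). Section 8 has one sensitivity analysis, which concerns missing data only.

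Table 3 in Appendix 3 reports, within each moderator level, a column whose heading begins "Group 2 – Group 1 Mean (95% CI", and one interaction p-value per model. That makes 2 outcomes x 3 moderators x 2 levels = 12 within-level intervals and 6 interaction p-values.

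The planned size is "556 participants". Section 4 fixes one moderator by quota: "Have (n=278), or have not (n=278), experienced any activity-related knee joint pain in the past 3 months". No split is fixed for education or care-seeking.

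**The concern.** A within-level interval from an interaction model uses the residual variance of the whole model, not of that level. On a 0-10 scale, a level whose mean sits near one end tends to have less spread, so unequal variance can arise from the scale alone. The interval is then too narrow in the more variable level and too wide in the other. If the two levels also differ in size, the interaction test itself can reject too often or too rarely.

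Knee-pain moderation is a stated secondary objective. Section 7.2 also asks readers to weigh unadjusted results by their effect sizes, intervals and p-values, and read in that spirit, the Table 3 intervals should have the coverage they claim. A check with no stated consequence also leaves the response to a bad plot open until the results are known.

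**Working it through.** **The plan's own figures.** 278 + 278 = 556, which agrees with the planned sample size. The plan has "adjusted the alpha for each primary outcome to 0.025 to give an overall alpha of 0.05 across both outcomes", and 0.025 + 0.025 = 0.05. The SAP gives no SD, effect size or power, so there is nothing else to reproduce.

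**Inputs.** From the SAP: N = 556, knee pain split 278/278, scores 0-10. Assumed, because the SAP does not give them: 1:1 arms (Section 1 says only that participants are "randomly allocated to one of two groups"), residual SDs s1 and s0 in the two moderator levels, share q of level 1, and, for the simulations, latent means, SDs and correlation.

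**Formulas.** With 1:1 arms and n_j people in level j:
- pooled variance: sp^2 = q*s1^2 + (1-q)*s0^2
- variance the model uses for the effect in level j: 4*sp^2/n_j; true variance: 4*s_j^2/n_j
- coverage of the nominal 95% interval: 2*Phi(1.96*sp/s_j) - 1
- interaction variance: the sum of the two level variances, in the model and in truth

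**Within-level intervals, 50:50, SD ratio 1.25.** Take s1 = 1.25 and s0 = 1. Then sp^2 = (1.5625 + 1)/2 = 1.281 and sp = 1.132.
- More variable level: 1.96 x 1.132/1.25 = 1.775, coverage 0.924.
- Other level: 1.96 x 1.132 = 2.219, coverage 0.973.
- At a ratio of 1.5 the figures are 0.904 and 0.988.

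**Interaction test, 50:50 (knee pain).** In units of 4/N, the model variance is sp^2 x (2 + 2) = 2*s1^2 + 2*s0^2, which equals the true variance. Type I error is 0.050 at every SD ratio; simulation gave 0.048-0.055.

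**Interaction test, 30:70, SD ratio 1.25.** 1/0.3 + 1/0.7 = 4.762.
- Smaller level more variable: sp^2 = 0.3 x 1.5625 + 0.7 = 1.169; model 1.169 x 4.762 = 5.57; truth 1.5625/0.3 + 1/0.7 = 6.64; 1.96 x sqrt(5.57/6.64) = 1.795; error 0.073.
- Smaller level less variable: the two variances change places; 1.96 x sqrt(6.64/5.57) = 2.140; error 0.032.

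Other cases, with the smaller level more / less variable:

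| Split | SD ratio | Interaction error |
|---|---|---|
| 40:60 | 1.25 | 0.061 / 0.041 |
| 30:70 | 1.5 | 0.093 / 0.022 |
| 20:80 | 1.25 | 0.086 / 0.025 |
| 20:80 | 1.5 | 0.121 / 0.013 |

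**Can the bounded scale alone produce such ratios?** Simulation: N = 556, 4,000 replicates, scores rounded and clipped to 0-10, latent correlation 0.6, latent SD 2.5 in both levels, no group effect. The Monte Carlo standard error at 5% is sqrt(0.05 x 0.95/4000) = 0.003.
- Latent means 6 v 9: residual SDs 1.92 and 1.51 (ratio 1.27). At 50:50, coverage 0.919-0.923 and 0.976, interaction error 0.051. At 30:70, interaction error 0.074 or 0.031.
- Latent means 6 v 8: residual SDs 1.92 and 1.70 (ratio 1.13). At 50:50, coverage 0.935 and 0.962.
- Equal means and SDs: everything nominal.

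A separate simulation under the same assumed correlation and latent SD gave 50:50 coverage of 0.928 and 0.977 (means 6 v 9) and 0.938 and 0.958 (means 7 v 8). Its interaction error was 0.058-0.064 at 30:70 with the smaller level more variable.

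**Primary tests.** With 1:1 arms inside each level, the true variance of the overall group difference is the same weighted average that the model uses. Simulated error was 2.2-3.0% at a nominal 2.5%.

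**With robust errors.** In the first simulation, HC3 gave coverage 0.939-0.956 and interaction error 0.044-0.057 across all scenarios. In the second, HC1 (the form behind Stata's vce(robust)) and HC3 both gave coverage 0.944-0.958 and interaction error 0.041-0.055.

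**The case against.** The strongest reply is that the one moderator named in the objectives is knee pain, and its interaction test is sound. A reader might infer from the pooled variance that all six interaction p-values are unreliable, or that knee-pain moderation could be created or hidden by it. The SAP does not support that: the 278/278 quota makes the pooled variance equal to the average of the two level variances. This part of the reply stands in full, given about 1:1 arms and little loss to the complete-case set that Table 3 uses. Only the knee-pain within-level intervals remain exposed.

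It can also be said that education and care-seeking appear in no objective, only in Section 7.1.2 and Table 3. Further, the moderation aim is worded as exploration, Section 7.2 calls the secondary outcomes exploratory and unpowered, and the SAP gives no data to show that variances or splits will be unequal. All of this is true and limits the weight of the point. It does not make the reported intervals right if the variances do differ.

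Finally, leaving the response to diagnostic plots to the statistician is common practice, and the analyst is blind to group name. Blinding limits choosing a method to favour an arm, and a change of standard error leaves every point estimate as it was. But the analyst can still see the size of each interaction, and the SAP does set a fallback for its ordinal model.

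**Conclusion.** The concern holds as a minor point. If residual SDs differ between moderator levels, the 12 within-level intervals in Table 3 miss 95% coverage: about 92-93% and 98% at 50:50 with one level near the scale end, and about 94% and 96% for smaller gaps. The four interaction p-values for education and care-seeking can be somewhat too small or too large, roughly 3-7% at a nominal 5% for a 30:70 split; more extreme splits or SD ratios would widen that range. The direction cannot be known in advance.

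The two knee-pain interaction p-values and the two primary comparisons are not affected, assuming about 1:1 arms. Every magnitude depends on assumed SDs, means, correlation and splits. With equal means and variances there is no error at all, so the SAP does not show that miscalibration will occur, only that nothing in it guards against it.

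**What to change.** Add one sentence to Section 7.1.2: the six moderator models reported in Table 3 use heteroscedasticity-robust standard errors (Stata vce(robust) or HC3, which perform equivalently at this sample size) as the prespecified analysis, and the plots of residual spread serve as description and do not change the model. The primary models need no change on this account.

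The cost is one Stata option and one sentence. Point estimates stay the same. If the variances are in fact equal, the intervals are slightly less precise than the pooled ones.

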### LIST OF TABLES/FIGURES/LISTINGS

Number	Title – analysis set
Table 1	Baseline characteristics of participants by group, reported as mean (standard deviation) unless otherwise stated.
Table 2	Summary measures and between-group mean differences [95% CI] or odds ratios/relative risk ratios [95% CI] for each outcome as appropriate.
Table 3	Moderation of the effect of the removal of pathoanatomical content in knee osteoarthritis educational information on primary outcomes using complete case data.
Table 4	Process measures.
Appendix 1	Baseline characteristics of participants who did and did not complete both primary outcomes, reported as mean (standard deviation) unless otherwise stated.

Table 1. Baseline characteristics of participants by group, reported as mean (standard deviation) unless otherwise stated.

Domain	Group 1 [N = xxx]	Group 2 [N = xxx]
Age (years)		
Gender, n (%)		
Male		
Female		
Transgender male		
Transgender female		
Non-binary		
Other / Prefer not to say		
Ethnicity, n (%)		
Australian/New Zealander		
Aboriginal and Torres Strait Islander		
European		
Asian		
Other Oceania		
North African & Middle Eastern		
Sub-Saharan Africa		
North American		
South American		
State/territory, n (%)		
Australian Capital Territory		
New South Wales		
Northern Territory		
Queensland		
South Australia		
Tasmania		
Victoria		
Western Australia		
Height (m)		
Weight (kg)		
Body mass index (kg/m  )		
Highest education level, n (%)		
Primary school		
Secondary school		
Trade or trade certificate		
University or tertiary institute		
Higher university degree		
Don't know/unsure		
Financial situation, n (%)		
Find it a strain to get by from week to week		
Have to be careful with money		
Able to manage without much difficulty		
Quite comfortably off		
Very comfortably off		

Prefer not to answer

Participation in regular exercise/physical activity, n (%)

None

1 time per week

2-3 times per week

4-5 times per week

6+ times per week

Ever sought care for knee pain from any healthcare provider, n (%)

Activity-related knee pain in the last 3 months, n (%)

Joint with knee pain, n (%)

Left knee only

Right knee only

Both knees

Sought formal treatment for knee pain, n (%)

Self-reported knee pain (NRS)

Self-reported physical function (NRS)

Prior knee surgery, n (%)

Regular pain relief for musculoskeletal condition, n (%)

Ability to read and understand written health information#,  
median (IQR)

---

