IQR: interquartile range (25th to 75th percentile); NRS: numerical rating scale ranging from 0 ('no pain' or 'no interference') to 10 ('worst pain possible' or 'maximal interference with function').

#Rated using a 5-point scale with terminal descriptors of 1='always difficult' to 5='always easy'.

Table 2. Summary measures and estimated between-group mean differences [95% CI] or odds ratios/relative risk ratios [95% CI] for each outcome as appropriate.

Outcome	Baseline, mean (SD)		Post-intervention ^ , mean (SD)		Within-group change a , mean (SD)		Between-group difference in post-intervention scores (n=xxx)	
	Group 1 (n=xxx)	Group 2 (n=xxx)	Group 1 (n=xxx)	Group 2 (n=xxx)	Group 1 (n=xxx)	Group 2 (n=xxx)	Mean b [95% CI]	P-value
Primary outcomes*								
Belief x-ray is necessary for diagnosis c								
Belief joint replacement surgery is necessary at some stage c								
Secondary outcomes								
Belief exercise and physical activity is helpful d,¥								
Belief exercise would damage knee c,β								
Belief medication is helpful c,¥								
Belief x-ray is necessary to determine treatment c,*								
Osteoarthritis Knowledge d,§								
	Baseline, n (%)		Post-intervention, n (%)		Between-group (n=xxx)			

	Group 1 (n=xxx)	Group 2 (n=xxx)	Group 1 (n=xxx)	Group 2 (n=xxx)	Odds ratio f [95% CI]	P-value	Relative risk ratio g [95% CI]	P- value
Level of concern h					OR [95% CI]	P	–	–
1 = Not at all concerned					–	–	REFERENCE	–
2 = A little concerned					–	–	RRR [95% CI]	P
3 = Quite concerned					–	–	RRR [95% CI]	P
4 = Very concerned					–	–	RRR [95% CI]	P

SD = standard deviation.

^ Correlation of post-intervention with baseline continuous outcome scores:

- Experimental group.
- Control group.

a Within-group change was calculated as post-intervention minus baseline for all outcomes.

b Mean (95% CI) difference in post-intervention scores between groups, adjusted for the outcome at baseline, estimated using separate regression models for each outcome.

c Negative values favour Group 2.

d Positive values favour Group 2.

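### The two primary outcomes are tested at alpha 0.025 but reported with 95% confidence intervals, so for 0.025 ≤ p < 0.05 (two-sided) the interval and the planned test disagree

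*SAP*

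**What the plan says.** Section 7.2 of the SAP gives the decision rule for the primary outcomes: "We have two primary outcomes and so have adjusted the alpha for each primary outcome to 0.025", with an overall alpha of 0.05 across the two. The same section leaves the secondary outcomes unadjusted and calls them exploratory.

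The confidence level is set elsewhere, and it is 95% for every outcome:

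- Section 7.1.1 (Aim 1): separate linear regressions for each primary outcome "will be used to estimate the between-group mean (95% confidence interval, CI) difference in post-intervention scores".
- Appendix 3, list of tables, title of Table 2: "Summary measures and between-group mean differences [95% CI] or odds ratios/relative risk ratios [95% CI] for each outcome as appropriate".
- Appendix 3, Table 2, footnote b: "Mean (95% CI) difference in post-intervention scores between groups, adjusted for the outcome at baseline". The column header above the primary rows also gives a 95% CI.

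No 97.5% interval appears anywhere in the SAP. No sentence says that the primary 95% intervals are descriptive. Table 2 puts primary and secondary p-values in one column and does not mark that the primary ones are to be compared with 0.025.

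**The concern.** A two-sided 95% interval corresponds to a two-sided test at 0.05, not at 0.025. The alpha split made in section 7.2 is carried into neither the primary analysis text nor the table in which the trial's answer will be read. If a primary p-value falls from 0.025 up to 0.05, Table 2 will show an interval that excludes zero for an outcome that fails the plan's own test.

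The SAP does not say which of the two then governs the wording of the conclusion. If that is settled only once the result is known, the choice is post hoc, and it concerns one of the two outcomes that answer the trial's question.

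**Working it through.** **Inputs**

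- Alpha 0.025 per primary outcome, 0.05 overall, two primary outcomes: section 7.2.
- Confidence level 95% for the primary effects: section 7.1.1 and Table 2 (title, column header, footnote b).
- Total sample size 556: section 1. It is used only for the degrees of freedom, 556 − 3 = 553 (intercept, group, baseline score), and for the example in step 3.
- Assumptions, because the SAP does not give them: two-sided tests, equal arms of 278, power, and the correlation between the two primary outcomes.

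**1. The plan's own figure.** 0.025 + 0.025 = 0.05, so the stated overall alpha is reproduced exactly (Bonferroni). If the outcomes are independent, the family-wise error is 1 − 0.975² = 0.0494. The split itself is correct.

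**2. Critical values.**

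| | Normal | t, 553 df |
|---|---|---|
| 95% CI, or two-sided test at 0.05 | 1.960 | 1.964 |
| 97.5% CI, or two-sided test at 0.025 | 2.241 | 2.248 |
| Ratio | 1.144 | 1.144 |

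The interval that matches the test is therefore about 14.4% wider. Interval and test disagree when |estimate/SE| lies between 1.964 and 2.248, that is, when 0.025 ≤ p < 0.05.

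**3. Example.** With 278 per arm, and ignoring the gain from baseline adjustment, SE = √(2/278) = 0.0848 SD units. Take estimate/SE = 2.1, so the estimate is 0.178 SD and p = 0.036.

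- Planned test at 0.025: fails.
- 95% CI: 0.178 ± 1.964 × 0.0848 = 0.012 to 0.345 SD, which excludes zero.
- 97.5% CI: 0.178 ± 2.248 × 0.0848 = −0.013 to 0.369 SD, which includes zero.

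**4. How often this can happen, per outcome.** Let δ be the true effect divided by its SE. Then P(0.025 ≤ p < 0.05) = [Φ(2.241 − δ) − Φ(1.960 − δ)] + [Φ(−1.960 − δ) − Φ(−2.241 − δ)].

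| True situation | δ | Probability |
|---|---|---|
| Null | 0 | 0.050 − 0.025 = 0.025 |
| Worst case, midway between the critical values | 2.10 | 0.112 |
| 80% power at 0.025 (assumed) | 2.241 + 0.842 = 3.083 | 0.869 − 0.800 = 0.069 |
| 90% power at 0.025 (assumed) | 2.241 + 1.282 = 3.523 | 0.941 − 0.900 = 0.041 |

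**5. Joint error under the null if intervals are used as tests.** This is the probability that at least one of the two intervals excludes zero, from the bivariate normal distribution. Independence gives 1 − 0.95² and 1 − 0.975².

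| Correlation (assumed) | Two 95% CIs | Two 97.5% CIs |
|---|---|---|
| 0 | 0.0975 | 0.0494 |
| 0.5 | 0.0907 | 0.0465 |
| 0.7 | 0.0835 | 0.0430 |

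The middle column describes a reader who replaces the planned test with the question whether the 95% interval excludes zero. It is not the type I error of the planned tests, which is the right-hand column.

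**The case against.** The strongest reply is that the plan's error control is intact. Section 7.2 ties the overall 0.05 to the tests. Section 7.1.1 uses the interval to estimate a difference, and nowhere does the SAP say that success is judged by whether an interval excludes zero. Each 95% interval also keeps its nominal 95% coverage for its own outcome. All of this stands. A reader might infer from the mismatch that the trial's overall alpha is really near 10%. The document does not support that: the 8.3% to 9.75% arises only if the intervals are used as tests.

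A second reply is that the p-value stands beside the interval, so the right decision can always be recovered. This is true for anyone who has section 7.2 in mind. It fails for a reader of Table 2 alone, because the shell does not give the threshold.

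A third is sidedness. The hypotheses in section 3.1 are directional, and the critical value of a one-sided test at 0.025 is 1.960, which a two-sided 95% interval would match in the hypothesised direction. The SAP does not state sidedness. Two-sided is the natural default for a trial described only as a "Two-arm, parallel groups superiority randomised controlled trial" with two-sided intervals, and the one-sided reading would make the overall 0.05 a one-sided level. This reply does not remove the point, but it makes the two-sided reading an assumption that must be declared.

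Last, 97.5% intervals are not the only remedy. A sentence that gives the primary 95% intervals a purely descriptive role would also remove the conflict. This stands too.

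**Conclusion.** The inconsistency is real and lies within the SAP: the confidence level of the primary intervals does not match the alpha at which the primary outcomes are judged, and nothing in the text reconciles them. Because the SAP fixes both levels itself, this is not a detail left to the protocol.

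Its weight is moderate, and it concerns reporting. Estimates, models, p-values, sample size and the planned test decisions are unaffected. It bites only if a primary p-value lands in the band from 0.025 up to 0.05, and the probabilities in step 4 of the working show that this is uncommon but not negligible. They rest on two-sided tests and a normal approximation, and the two power rows also rest on powers that the SAP does not state. It would be too strong to say that the trial fails to control its type I error, or that the analysis cannot go ahead without this change.

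**What to change.** - In section 7.1.1 and in Table 2 (title, column header and footnote b), give 97.5% CIs for the two primary outcomes. 95% CIs may stand beside them if labelled descriptive.
- Add a footnote to Table 2 that the p-values of the two primary outcomes are compared with 0.025.
- State in section 7.2 that the tests are two-sided. If one-sided tests are intended, say so, and say that the overall 0.05 is then one-sided.
- Keep 95% CIs for the secondary and moderator analyses, which the plan does not adjust for multiplicity.

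At minimum, if the 95% intervals are kept for the primary outcomes, add one sentence that they are for estimation only and that conclusions rest on p < 0.025, together with the footnote.

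The cost is a few lines of SAP wording and one table shell, and primary intervals about 14% wider. No change to data, models or sample size is needed. The edit should be made before the group comparisons are seen.
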